10. STATISTICAL CONSIDERATIONS

It is known that tumor pathologic variables, such as invasive ductal carcinoma, high tumor grade and high proliferative activity, are associated with a better response to neoadjuvant treatment. It is also known that triple-receptor negative and HER2 positive tumors respond best to cytotoxic and Herceptin-based regimens, respectively. To estimate the predictive value of these parameters as well as newly acquired hemoglobin parameters from US-guided NIR system, we have developed a logistic regression model which can be used to describe the relationship of several predictor variables X_1, X_2, \dots, X_k to a dichotomous response variable Y , where Y is coded as 1 (responder) or 0 (non-responder) for its two possible categories. We also assess the overall quality of the prediction models through the ROC curves and the area under ROC (AUC). For this purpose, all parameters will be inputted to the prediction model to estimate the predict power on final pathological response. Once the model is validated from the new patient data, it can serve as a guideline for predicting patient response to neoadjuvant treatment.

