For ER+ and Her2- patients, recent studies have shown that a pathological complete response is rarely achieved by neoadjuvant chemotherapy. At current practice, most of the patients were treated by hormone therapy which is a much more prolonged treatment than neoadjuvant chemotherapy. We do not plan to immediately recruit patients who will be treated by hormone therapy. In our pilot study, we had a total of 22 patients with ER+ and HER2- cancers and have obtained statistical significance based on tHb difference between responder and non-responder groups at the pre-treatment. We also obtained statistical significance based on %tHb at the end of cycle 1. The estimated sample size needed at

significance level of $\alpha = 0.01$ (power 0.99) using difference in mean values and pooled standard deviations of two responder groups at pre-treatment and end of the cycle 1, suggests that 12 patients are required for this group of patient in the new study. Again, MINITAB two sample t-test was used for calculations.

Based on our past experience, about 20% of the patients may either go to early surgery or drop the study due to side effects of treatment. With the 60 planned patients, we expect to have approximately 50 patients who will complete the study. Based on the patient pool at Washington University, we expect ~18 HER2 positive patients, ~19 triple receptor negative patients in the next two years of the award. The rest will be ER+ and HER- patients.

The adequate sample size of HER2 positive patients and triple receptor negative patients will allow us to evaluate the observation that the best time windows for predicting early response based on %tHb changes is within the first cycle for HER+ patients, and the best window for predicting early response is within the first three cycles for triple receptor negative patients. The new data that will be obtained at the end of day 7 may offer new insight into early tumor responses of these two major treatment groups.

Although the Taxol-based and Herceptin-based regimens have an important place in the treatment of breast cancer, many alternatives or new anti-cancer regimens are equally interesting and acceptable. We anticipate that a small population of patients of the proposed large patient cohort will be treated with novel regimens as these new treatments become available for clinical trials, and the results for these regimens can be used as pilot data for the efficacy of the new regimens.

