10.3. Data Analysis

The multivariate logistic regression models will be used to model the binary primary endpoint. The receiver operating characteristics (ROC) curve analysis will be applied based on the fitted multivariate logistic model to evaluate the predictive ability of tumor vascularity parameters measured by NIR/US at baseline and at different treatment cycles including total, oxygenated and deoxygenated hemoglobin concentrations (abbreviated as tHb, oxyHb, deoxyHb, respectively) without and with inclusion of classic pathological variables including tumor histology, estrogen and progesterone receptor status, HER2

status, Ki67 proliferation index, Nottingham score, mitotic index, intrinsic subtype. To summarize the resulting predictive ability, the area under ROC (AUC) with DeLong's method for confidence interval calculation and the sensitivity, specificity, positive and negative predictive value corresponding to an optimal cutoff will be derived. Two models will be compared based on their AUCs based on the DeLong's method and the likelihood ratio test. To robustly assess the predictive ability, the cross validation (CV) procedure will be applied: at each CV, 2/3 of the observations will be used to train the model while the remaining will be used to validate the model.

For the exploratory neoadjuvant endocrine cohort, the analysis will also include correlation with PEPI scores.

For the additional aim, correlate tHb with enhancement on CEM.

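### The planned model comparison tests what pathology adds to NIR/US, not what NIR/US adds to pathology, and DeLong's p-value on nested fitted models does not hold its level

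*Combined protocol and SAP*

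**What the plan says.** Section 10.3 models response (Miller-Payne grade 4/5 against 1-3, Section 10.2) by logistic regression. It evaluates the NIR/US parameters tHb, oxyHb and deoxyHb "without and with inclusion of classic pathological variables including tumor histology, estrogen and progesterone receptor status"; the list goes on to HER2, Ki67, Nottingham score, mitotic index and intrinsic subtype, eight variables in all. On the scores to be used: "The receiver operating characteristics (ROC) curve analysis will be applied based on the fitted multivariate logistic model". On the comparison: "Two models will be compared based on their AUCs based on the DeLong's method and the likelihood ratio test". The next sentence turns to validation: "To robustly assess the predictive ability, the cross validation (CV) procedure will be applied", with two thirds of the observations for training and one third for validation. It does not say whether the compared AUCs come from that procedure.

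Section 10 presents the pathology variables as established predictors, for example "It is also known that triple-receptor negative and HER2 positive tumors respond best to cytotoxic and Herceptin-based regimens, respectively". Its stated aim covers both sets: "To estimate the predictive value of these parameters as well as newly acquired hemoglobin parameters from US-guided NIR system". The only model it describes is a single one in which "all parameters will be inputted to the prediction model to estimate the predict power on final pathological response". Neither section names a model with pathology alone, and no significance level is given for the comparison.

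**The concern.** There are two separate problems.

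The first is the contrast. NIR alone and NIR plus pathology differ only by the pathology terms, so a significant result is evidence about pathology. Section 10 already takes it that pathology predicts response. The open question is what the hemoglobin parameters contribute beyond it, and that needs a pathology-only reference. Without one, a significant comparison could be reported as support for the NIR/US model when it reflects pathology alone, or merely the number of pathology terms added.

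The second is the test. If both AUCs are computed on the patients used to fit the models, the smaller model is nested in the larger. Added terms then tend to raise the in-sample AUC even when they carry no information. When the added terms are truly useless, the two score sets converge and the normal approximation behind DeLong's test fails. The likelihood ratio test (LRT) is the standard nested test, but unpenalised it is too liberal with this many terms and so few responders.

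**Working it through.** **The plan's own figure.** The plan gives no power, level or sample size for this comparison. The only figure to reproduce is the number of completers. Section 10.1 says that "about 20% of the patients may either go to early surgery or drop the study due to side effects of treatment", so 60 × (1 − 0.20) = 48, against the stated figure of about 50. This agrees within two patients.

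**Inputs**
- n = 48, from the line above (range 40-50).
- Responders: no overall grade 4/5 rate is given. Assumed 40%, so 0.40 × 48 = 19.2, taken as 19 (range 15-24). The only 40% in the plan is a complete-response rate for triple-negative disease (Section 10.1).
- NIR terms: 3, for one time point. Pathology terms: the 8 listed with one coefficient each; 2 and 4 were also tried.
- Level 0.05, assumed. The 0.01 in Section 10.1 belongs to the subgroup t-tests.
- Independent normal predictors, assumed. Each block has joint AUC 0.50 (useless) or 0.80. From AUC = Φ(δ/√2), an AUC of 0.80 means δ = 1.414 × 0.842 = 1.19 standard deviations.

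The full model has 3 + 8 = 11 terms, or 19/11 = 1.7 responders per term.

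**Tests.** LRT: 2 × (log-likelihood of the larger model − that of the smaller), referred to χ² with as many degrees of freedom as added terms. DeLong: the difference in AUC of the fitted scores divided by its paired standard error. There were 1,500 trials per main scenario, so the Monte Carlo standard error of a 22% rate is √(0.22 × 0.78/1500) = 1.1 points. Range scenarios used 800 trials each.

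**Comparison as written (NIR against NIR plus pathology), percentage significant**

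| NIR AUC | Pathology AUC | Pathology terms | DeLong | LRT |
|---|---|---|---|---|
| 0.50 | 0.80 | 4 | 79 | 91 |
| 0.50 | 0.80 | 8 | 93 | 86 |
| 0.80 | 0.50 | 8 | 22 | 20 |
| 0.80 | 0.80 | 4 to 8 | 45-72 | 79 |

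Over the ranges of n and responders, the first two rows together span 72-94% (DeLong) and 82-93% (LRT). The third row spans 18-27% and 17-30%. Repeat simulations under the main assumptions gave 19-22% and 15-17% for the third row.

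In the third row the in-sample AUC rises by 0.07 on average when the useless pathology terms enter. The cross-validated AUC (2/3:1/3 splits) falls by 0.09. With only two to four useless terms added, DeLong rejects in 0.5-3% and the LRT in 7-11%, so DeLong's error changes direction with the number of terms.

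**Not only a small-sample effect.** At n = 1,000, adding eight useless terms to three gives DeLong rejection rates of 20%, 9% and 7% at base AUC 0.5, 0.7 and 0.8. Adding one useless term to one gives 0-0.3%. The LRT stays at about 4-7%.

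**Proposed pair (pathology against pathology plus 3 NIR terms), NIR useless, 2 to 8 pathology terms.** DeLong rejects in about 1-4% and the unpenalised LRT in 6-19%. A permutation LRT, which permutes the NIR residuals on pathology (600 trials, 99 permutations each), rejects in 3.5% with 2 pathology terms and 3.7% with 8. With a single NIR term and 2 pathology terms it rejects in 5.5%. With both blocks at AUC 0.80 and 2 pathology terms, its power is 0.72, or 0.86 with a single NIR term.

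**The case against.** The strongest reply is that Section 2 does not list added value over pathology as an objective. The primary objective is to evaluate NIR/US as a predictor, and the NIR-alone AUC with its confidence interval addresses that. This stands, and it limits the defect to what the comparison can conclude.

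It can also be said that the 22% rests on eight useless pathology terms, a null that Section 10 itself rejects, and that wrongly crediting pathology does little harm. That is fair for the false-positive figure. It does not touch the first problem: with useless NIR/US and informative pathology, the setting Section 10 makes plausible for pathology, the comparison is nearly always significant.

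The plan also names the LRT and cross-validation. The LRT tests the same contrast and is itself liberal here. Cross-validation would expose the optimism if it were applied to the compared AUCs, but the text attaches the ROC analysis to the fitted model and leaves the link unstated. If held-out scores were meant, DeLong's in-sample problem does not arise in that form, and the plan should say so.

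Finally, the remedy has limited power. With all eight pathology variables, three NIR terms and both blocks at AUC 0.80, permutation LRT power was about 0.46 (200 trials); with four pathology terms, about 0.66. With NIR at AUC 0.70 it was about 0.37 with two pathology terms and 0.23 with eight. This is a consequence of the sample size. It argues for few terms and for an estimate with an interval, since a non-significant result would say little.

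**Conclusion.** The concern holds. The wrong contrast and the missing pathology-only model follow from the text on its natural reading and need no simulation. The qualification is that the plan never defines the two models.

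The miscalibration depends on the AUCs being compared on fitted scores. It runs to about 20% false positives when the eight listed variables are added, and well below 5% for DeLong when few are. These sizes rest on the assumed 0.05 level, responder rate, independent normal predictors and one coefficient per variable. Multi-level factors or several cycles in one model would add terms and would be expected to worsen the overfitting.

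This is a point that should be fixed, held with medium confidence. It limits the comparison and not the primary NIR-alone estimate.

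**What to change.** In Section 10.3:

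1. Define the compared models and the imaging time point they use.
2. Add a pathology-only reference model with a small, pre-specified set of terms.
3. Make pathology-only against pathology plus NIR the pre-specified comparison.
4. Test it with a permutation or penalised LRT at a stated level, and drop the DeLong p-value for nested models.
5. Report the cross-validated or optimism-corrected AUC difference with a bootstrap interval.
6. Keep the NIR-alone AUC with its confidence interval as planned.

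The cost is SAP wording and one extra model fit on data already collected; enrolment and visits do not change. The p-value may be less favourable. With 2 pathology and 3 NIR terms, the permutation LRT has power 0.72 against an apparent 0.81 for the unpenalised LRT, whose level is inflated. Because power falls further with more terms or a weaker NIR effect, the interval should carry the interpretation.

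### Section 10.3 tests nested models with DeLong's AUC test, which does not hold its level there, and gives no rule for choosing between it and the likelihood ratio test

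*Combined protocol and SAP*

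**What the plan says.** Section 10.3 models the binary response (Miller-Payne grade 4/5 against 1–3) by logistic regression. On the source of the ROC results it says: "analysis will be applied based on the fitted multivariate logistic model to evaluate the predictive ability of tumor vascularity parameters". This is done for the NIR/US parameters both alone and together with a pathology set, in these words: "without and with inclusion of classic pathological variables including tumor histology, estrogen and progesterone receptor status, HER2". The other items named are Ki67, the mitotic index, the Nottingham score and the intrinsic subtype, which makes eight variables in all. Section 10 indicates no selection among them: "all parameters will be inputted to the prediction model to estimate the predict power on final pathological response".

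The comparison is then stated in one sentence: "Two models will be compared based on their AUCs based on the DeLong's method and the likelihood ratio test". A cross-validation follows, in which "at each CV, 2/3 of the observations will be used to train the model while the remaining will be used to validate the model".

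The section does not define the two models further. It gives no alpha for the comparison, does not say which test decides if they disagree, and does not say whether DeLong's test uses apparent or cross-validated AUCs. The wording about the fitted model points to apparent AUCs.

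On numbers, Section 10.1 says "With the 60 planned patients, we expect to have approximately 50 patients who will complete the study", after noting that "about 20% of the patients may either go to early surgery or drop the study due to side effects of treatment".

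**The concern.** The model with the pathological variables contains every term of the model without them. If those variables add nothing, the fitted scores of the two models converge, and the AUC difference and its variance both shrink towards zero. DeLong's statistic refers the difference to a normal distribution with a non-degenerate variance, so its reference distribution is wrong. Separately, when many terms are added and the AUCs are computed in the fitting patients, the larger model's AUC rises by overfitting alone, and DeLong's test does not allow for that.

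The two faults push in opposite directions. With one or a few added terms the test hardly ever rejects. With many added terms it rejects too often. With two tests named and no hierarchy, either result could be reported as the answer on whether pathology adds to NIR/US.

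**Working it through.** **Sample size.** 60 × (1 − 0.20) = 48, which agrees with the plan's approximately 50 completers. If the 10 endocrine patients are part of the 60, the chemotherapy completers number about 50 × 0.80 = 40.

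**Terms against events.** The documents give no overall responder rate. At an assumed 40%, 48 × 0.40 ≈ 19 responders. Two base terms (tHb is the sum of oxyHb and deoxyHb, so one time point carries two independent parameters) plus eight added terms make ten coefficients, or about 1.9 responders per coefficient. If intrinsic subtype has four levels (assumed), the added set has about 10 degrees of freedom.

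**Tests compared.**
- DeLong: z = (AUC₂ − AUC₁) / √V, where V is the paired variance from the placement values of responders and non-responders. Reject if |z| > 1.96.
- Likelihood ratio test (LRT): 2(ℓ₂ − ℓ₁) against chi-square with q degrees of freedom, where q is the number of added terms.

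**Main simulation.** n = 48, 40% responders, two base predictors with AUC 0.75, independent normal predictors, two-sided 5%, up to 3,000 runs per setting. Ranges are across repeated runs.

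| Added variables | DeLong rejects | LRT rejects |
|---|---|---|
| 1, worthless | 0.1–0.3% | 6.5% |
| 8, worthless | 20–22% | about 14% |
| 9, worthless | 30% | about 18% |
| 1, useful (difference 0.8) | about 11% | 67–70% |
| 9, one of them useful (0.8) | 59–61% | 48–52% |

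With eight worthless variables that are correlated and half of them binary, DeLong's test still rejects 22%; with ten such variables, 35%.

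**Does it go away with more patients?** At n = 400, DeLong's test rejects 0–0.1% with one worthless variable and 12–13% with nine. At n = 500 (45% responders) it rejects 0.1% with one and 18% with ten, while the LRT is near nominal at 5.9% and 6.3%. The LRT's inflation is therefore a small-sample effect; DeLong's errors persist.

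**Where the excess rejection comes from.** When the same fitted models are scored in fresh patients, DeLong's test declares nine noise variables an improvement in 0.2% of runs, at n = 48 and at n = 400. The in-sample figures are 30% and 13%. So the excess is largely in-sample optimism. With ten noise variables at n = 50, the apparent AUC rises from 0.76 to 0.87 while the hold-out AUC falls from 0.73 to 0.62.

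**Sensitivity.** n = 50, 45% responders, base AUC 0.60 to 0.85, no added value:

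| Added variables | DeLong | LRT |
|---|---|---|
| 1 | 0.1–0.2% | 5.6–6.7% |
| 3 | 0.9–2.5% | 7.6–7.9% |
| 8 | 13–30% | 10–18% |
| 10 | 29–48% | 15–26% |

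With a real added marker of AUC 0.70, DeLong's power is 4–22% with one added variable (LRT 53–73%) and 36–80% with 8–10 added, much of the latter being overfitting. At n = 40 with ten worthless variables, DeLong's test rejects 42% and the LRT 26%.

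**Disagreement between the tests.** With one useful added variable they disagree in 57–59% of runs. With nine added variables they disagree in 15–19%.

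**Check of the remedy.** With eight worthless variables, the LRT with a permutation reference rejects 5.7% (300 runs, standard error √(0.057 × 0.943 / 300) = 1.3 points), against about 13% with chi-square.

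**The case against.** The same sentence already names the LRT, the standard test for nested models, and the next adds cross-validation, so the plan does not rest on DeLong's test alone. That is right, and it narrows the point: the gap is an unsuitable test placed beside a suitable one with no hierarchy. Cross-validation does not close it, because the text does not connect it to either test. Applying DeLong's test to a single one-third hold-out (about 16 of 48 patients) removes the false positives (at most 2.6%) but finds an improvement in at most 13% of runs when an added marker of AUC 0.70 is real.

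A reader might infer that real added value will almost always be missed. The documents do not support that for this plan. It holds when one or a few variables are added, but the plan lists eight and enters them all. There DeLong's test rejects more often than the LRT, and the dominant risk is noise declared useful.

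A reader might also take the whole fault as a consequence of nesting, separate from scoring in the fitting patients. That fits the conservative half. The false-positive half is largely in-sample optimism, as the fresh-patient result shows.

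Finally, moving to the ordinary LRT is not a full cure: with 8–10 added degrees of freedom at about 50 patients it is inflated as well.

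**Conclusion.** The point stands as a should-fix. For nested models fitted and scored in the same patients, DeLong's test has the wrong error rate: 0.1–0.3% for one worthless added variable and about 20–30% for eight or nine, at a nominal 5%. The chi-square LRT is also too liberal for a set of that size, at about 14–18%. The plan does not say which result governs.

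It is not a must-fix. A reader might infer that the primary objective or the sample size is undermined, but Section 10.1 sizes the study on subgroup t-tests of tHb, and no stated decision depends on this comparison. As written, the contrast also asks what pathology adds to NIR/US. The reverse question would need a pathology-only base model.

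Only the completer number comes from the documents. The responder rate, base AUC, two base predictors, 5% alpha and independent normal predictors are assumptions. Section 10.3 allows several time points, and real pathological variables are correlated and partly categorical, so the exact figures would change. The direction held in every setting tried.

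**What to change.** In Section 10.3:

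1. Define the two models, with the terms and degrees of freedom in each.
2. Remove the DeLong p-value for this nested comparison.
3. Make the LRT the single test of added value, at a stated alpha. Use a permutation reference distribution (permuting the pathological variables jointly as a block), or restrict the added set to a few degrees of freedom. If the block is clearly correlated with the NIR/US parameters, simulating outcomes from the fitted base model is an alternative reference.
4. Report the AUC difference descriptively, with an optimism-corrected bootstrap or cross-validated interval.

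The cost is a wording change and a few lines of code, with no added patients or data. The downside is that the AUC difference no longer carries a p-value.

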10.1. Sample Size Calculations

For triple receptor negative breast cancers, recent studies have shown that 40% of the patients achieved pathologic complete response [25]. For Her2 positive breast cancers, recent studies have demonstrated that new anti-cancer regimens trastuzumab (Herceptin) plus lapatinib (Tykerb), or with trastuzumab plus pertuzumab (Perjeta) have resulted in a statistically significantly larger number of patients achieving pathologic complete response [25]. From our pilot study, we have observed a 25% change in total hemoglobin level when compared to pre-treatment baseline (%tHb) between the responder (Miller-Payne grades 4-5) and non-responders (Miller-Payne grades 1-3) at the end of cycle one. However, no statistical test was performed because of the small sample size ($n=5$) for this subgroup. Based on our earlier pilot data of response at end of cycle 1, $n=5$, the estimated sample size needed at significance level of $\alpha = 0.01$ (power 0.99) using difference in mean values and pooled standard deviations of two responder groups obtained from the pilot data of five patients at the end of cycle 1 suggests that 18 patients are required for the Her2 positive group in the new study. We observed an even greater difference of 34.1% in total hemoglobin level when compared to baseline between the two responder groups for triple receptor negative patients at the end of cycle 3. Again, no statistical test was performed because of the small sample size ($n=6$). The estimated sample size needed at significance level of $\alpha = 0.01$ (power 0.99) using difference in mean values and pooled standard deviations of two responder groups obtained from these 6 patients at the end of cycle 3, suggests that 19 patients are required for the triple receptor negative group in the new study. MINITAB two sample t-test was used for calculations.

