For the exploratory cohort, we plan to enroll 10 patients.

In summary, sixty eligible patients will be enrolled and ~50 patients are expected to complete the study. Based on the patient pool at Washington University, we expect to recruit ~18 HER2-positive patients, ~19 triple negative patients, and the rest may be ER-positive and HER2-negative patients.

We will thereby begin to benchmark the optical signature of neoadjuvant treatment response of subsets of breast cancer based on molecular phenotype.

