10.2. Primary Endpoint

The primary endpoint is pathologic response based on the Miller-Payne grading system (See Section 7 for description on grade 1~5). Patients will be grouped into responder (grade 4/5) and non-responder (grade 1~3) for statistical analysis.

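### With about 48–50 completers, the default chi-square p-value for the likelihood ratio test in Section 10.3 rejects too often: about 12–23% instead of 5% under plausible one-scan models

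*Combined protocol and SAP*

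**What the plan says.** Section 10.3 models the binary response by multivariable logistic regression. The predictors are total, oxygenated and deoxygenated hemoglobin at baseline and at later cycles, without and with eight pathological variables: histology, ER, PR, HER2, Ki67, Nottingham score, mitotic index and intrinsic subtype. It then states: "Two models will be compared based on their AUCs based on the DeLong's method and the likelihood ratio test". The outcome is fixed in Section 10.2: "Patients will be grouped into responder (grade 4/5) and non-responder (grade 1~3) for statistical analysis".

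Section 10 adds that "all parameters will be inputted to the prediction model to estimate the predict power on final pathological response". On size, Section 10.1 says "With the 60 planned patients, we expect to have approximately 50 patients who will complete the study", after noting that "about 20% of the patients may either go to early surgery or drop the study due to side effects of treatment". It also says "For the exploratory cohort, we plan to enroll 10 patients", without saying whether these ten are part of the 60.

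The plan does not give the coding of the pathological variables, the number of NIR/US terms per model, any variable selection or penalty, a significance level for this test, or a reference distribution for its statistic.

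**The concern.** Where nothing else is specified, software takes the p-value of a likelihood ratio test from the chi-square distribution, with degrees of freedom equal to the number of added coefficients. That approximation needs many patients per coefficient. With about 12 slopes fitted to about 48 patients, maximum likelihood fits noise, and the statistic exceeds its chi-square distribution even when the added block carries no information.

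This is one of only two formal model comparisons in the plan. A nominally significant result could be reported as added predictive value when the data show only that the larger model is large for the sample. The point is separate from the validity of the DeLong comparison, and it would matter more if the likelihood ratio test became the governing comparison.

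**Working it through.** **Sample size.** 60 × (1 − 0.20) = 48, which agrees with the stated figure of about 50. If the ten endocrine patients are inside the 60, the chemotherapy completers number (60 − 10) × 0.80 = 40.

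**Responders.** No overall rate for grades 4/5 is given. The only rate is for complete response in triple-negative disease: "recent studies have shown that 40% of the patients achieved pathologic complete response". Assuming about 40% overall gives 48 × 0.40 ≈ 19 responders.

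**Coefficients (assumed).** Seven pathological variables at one coefficient each, plus intrinsic subtype at four levels (three coefficients), gives 7 + 3 = 10. One coefficient per variable gives 8. Total hemoglobin is the sum of its two components, so each scan supplies 2 independent NIR/US terms. Four scans (baseline and cycles 1–3) supply 8. The larger model then has 2 + 10 = 12 slopes with one scan (48 / 12 = 4 patients per slope) or 8 + 10 = 18 with four.

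**Method.** Simulate outcomes for which the added block has no effect. Fit both models by maximum likelihood, compute 2 × (log-likelihood of larger − log-likelihood of smaller), and count how often it exceeds the chi-square 95% point. There were three sets of runs:

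- A: subtype mix 18:19:11, 10 pathology terms, scans correlated 0.5, about 41% responders, 1,500 runs per setting.
- B: pathology as independent normals or as a correlated mix of binary and continuous variables. Responder rates were 30–50% in the main grid and 40% in the sensitivity and reverse runs, with 800–1,500 runs per cell. The strength of the smaller model's predictor was varied through its AUC.
- C: idealised independent normal predictors, 800–1,000 runs per cell.

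Monte Carlo standard error at a true rate of 20% is √(0.2 × 0.8 / 1500) = 1.0 point for 1,500 runs and √(0.2 × 0.8 / 800) = 1.4 points for 800.

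**Rejection rate at nominal 5%, added block null**

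| Setting | A | B | C |
|---|---|---|---|
| n = 48, 2 NIR/US, add 10 pathology | 21–23% | 15–23% (AUC 0.50–0.75); 28–35% (0.85); 37–47% (0.90) | 13–21% |
| n = 48, 10 pathology, add 2 NIR/US | 15–18% | 13–18% (AUC 0.50–0.75); 30% (0.85) | 12–16% |
| n = 48, 8 NIR/US, add 10 pathology | 54% | 33–77% (8–12 NIR/US terms) | 36–51% |
| n = 40, 2 NIR/US, add 10 pathology | 29% | 25–42% (AUC 0.50–0.85) | 20–26% |

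**Fewer pathology terms** (n = 48, 2 NIR/US terms, set B, AUC 0.50–0.85): 8 terms 15–21%, 6 terms 12–16%, 4 terms 9–11%, 2 terms about 8%. Set C gave 7–13% with 4–8 added terms.

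**Dependence on n** (set B, 2–3 NIR/US terms, 10 pathology terms, AUC 0.50–0.85): n = 40, 25–45%; n = 50, 14–31%; n = 60, 12–21%; n = 100, 8–11%; n = 200, 6–8%. The rate approaches 5% only at sizes well beyond this study.

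**At a 1% level** (set C, 2 NIR/US + 10 pathology, n = 48): 5–9%.

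**Summary.** The one-scan rows at n = 48, with a weak to moderate predictor in the smaller model (AUC up to 0.75) and 8–10 pathology terms, give about 12–23% over both directions.

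**Check of the remedy at n = 48.** The Firth-based parametric bootstrap rejected 4.0–4.8% with one scan and 5.8–9.3% with four (400 runs, 99 resamples). The chi-square reference on the same data rejected 17.5–23% and 43–55%. A further bootstrap check gave 3–4% (200 runs, 59 resamples).

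**The case against.** **Every figure rests on unstated choices.** This is true of the coding, the 5% level, the responder rate and the number and strength of the NIR/US terms. A reader might take 10 coefficients or 5% as facts of the plan. They are not: the only significance level stated, 0.01, belongs to the t-test sample sizes. A reader might also infer that the error rate is generally near 50%. That needs several scans entered together or a very strong NIR/US predictor. Section 10 leans towards entering everything, but Section 10.3 does not say that scans enter jointly. What survives is the direction: every setting examined at n = 48 gave more than 5%.

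**The stated comparison does not test the device.** This also stands. Section 10.3 adds pathology to NIR/US, so a reader who infers that the planned test would falsely credit NIR/US goes beyond the text. Section 10 moreover treats pathology as already known to relate to response, which makes the null less plausible in that direction. That known association does not settle whether pathology adds to NIR/US, and an inflated statistic overstates the evidence either way.

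**No success rule depends on this p-value.** Correct. The main summaries are AUC with its interval, sensitivity, specificity and predictive values, with cross validation on a 2/3–1/3 split. This limits the harm. It does not repair the p-value, because cross validation addresses predictive ability and not the reference distribution of the test.

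**The root cause is too many coefficients.** It is the same root. In set B, complete separation of the larger model occurred in up to 62% of runs with 2–3 NIR/US terms. Cutting terms reduces the inflation but does not remove it: about 7–16% remains with 4–6 pathology terms.

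**Conclusion.** The concern holds in this form: at about 48–50 completers, the chi-square reference that applies by default to the likelihood ratio test in Section 10.3 is not valid. With about 40% responders, a nominal 5% level and 8–10 pathology terms (all assumptions), the false-positive rate is about 12–23% with one scan's NIR/US terms. It is about 35–55% with several scans entered together and about 7–16% with 4–6 pathology terms. It is higher if only about 40 chemotherapy patients complete, or if the smaller model already predicts strongly.

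In the plan's stated order, a false positive credits pathology with value beyond NIR/US. If the reverse comparison were made, about 13–18% of null results would credit NIR/US.

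A reader might also infer that the test has no valid reference distribution at this size. That goes too far, since resampling supplies a usable one. The plan simply does not name it.

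**What to change.** In Section 10.3, keep the likelihood ratio statistic but take its p-value from a parametric bootstrap under the smaller model:

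1. Compute the observed statistic from maximum-likelihood fits of both models.
2. Fit the smaller model with Firth's penalty and use its fitted probabilities to simulate outcomes for the same patients, for example 2,000 times.
3. For each simulated data set, refit both models by maximum likelihood, as for the observed data, and recompute the statistic.
4. Set p to the share of simulated statistics at least as large as the observed one.

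The coding of the eight variables and the level of the test should be stated in the same place. Limiting each comparison to one scan is a separate analysis choice that this change does not require.

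The cost is a few sentences and some minutes of computing, with no new patients or data. The downside is that p-values become larger. If many scans enter jointly, the bootstrap may still run slightly above nominal (5.8–9.3% in the four-scan runs).
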